1. SYNOPSIS

The elderly patient demented in an acute geriatric department: pilot study, monocentric, randomized on the use of aromatherapy as a complementary treatment tool to psychopharmacology in psychological disorders and behavior (BPSD).

Rationale

Behavioral and psycological symptoms of dementia (BPSD) are a big issue for families, paramedics, physician and the patient itself (1,2,3,4).

In absence of universally recognized guidelines, the standard of treatment of these disorders involves the use of psychotropic drugs (typical/atypical neuroleptics, antidepressants, benzodiazepines) that are often found to have a reduce efficacy and induce a number of side effects such as sedation, impaired motor neurons slowdown, cardiac electrical alterations and extrapyramidal syndrome (5,6,7,8,9). In consideration of this, it is important to check for treating alternative ways, which can reduce psychological and behavioural disorders and at the same time can reduce the use of psychotropic drugs.

Concerning the aromatherapy [10], the therapeutic use of natural essential oils, there are decades of clinical experience, especially in France, accompanied by increasing scientific evidence with significant increase in publications regarding its use of psychological disorders and dementia-related behavior context (11,12,13,14).

Based on the available scientific publications, it has been therefore decided to use two essential oils (*Citrus sinensis, Lavandula angustifolia*) in environmental diffusion within the Geriatric Department of the Clinic Luganese Moncucco.

Objectives

Primary objectives: through the execution of the Neuropsychiatric Inventory – Nursing Home Version (NPI-NH), the neuropsychiatric and psychopathological symptoms of dementia patients will be evaluated in order to assess how the use of aromatherapy can improve the management of BPSD, reducing, where there is clinical indication, psychotropic therapy and secondary side effects. The score is considered positive if the presence of BPSD is greater than or equal to 1 (15, 16,17); the improvement of the score is represented from decrease of the NPI-NH respect to the initial assessment (19, 20).Performing neuropsychological tests is not an additional attention to enrolled patients, but it is part of clinical practice (18).

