
Nurses will be undergo to NPI – NH test within 48 hours after patient admission or at first appearance of BPSD **(T1), T2 (T1-3 days)** 3 days after enrollment, at **T3 (T1-6 days)** 6 days after enrollment, at **T4 (T1-12 days)** at 14th day. According to the same timing, NPI-NH will also be performed to the resident physicians, the nurses and the care assistants to assess the psychological distress. The NPI-NH test will be performed following the Good Clinical Practice.

The tests results performed to the two groups of patients will be considered in order to assess a possible reduction in BPSD. As the project is a pilot study, a descriptive analysis will be performed.

Here the schemes defined for treatment with aromatherapy and psychotropic drugs, according to scientific publications in the first case and scientific publications and Evidence Based Medicine in the second:

Aromatherapy

Route of administration: air diffusion with ultrasonic diffuser in a single room and for about an hour.

Doses:

- Citrus sinensis: 6 drops at 8, 12 and 18 in nebulization

and

- Lavender angustifolia: 6 drops 8 p.m. in nebulization

PRN PSYCOPHARMACOTHERAPY

Drug:

- in case of psychomotor agitation:

Haloperidol 1 mg PO 10 times in 24 hours

1 mg SC/IM 5 times in 24 hours

Reperidone 0.5mg - 2mg PO in 24 hours *Olanzapine* 2.5 mg – 5 mg PO in 24 hours

Clozapine 6.25 mg – 25 mg PO in 24 hours

Quetiapine 12.5mg - 150mg PO in 24 hours

- in case of sleep disturbance:

Valerian 1 tb - 2 tbs PO in 24 hours Melatonin 1 tb - 2 tbs PO in 24 hours Lorazepam 0.5 mg - 3mg PO in 24 hours Oxazepam 7.5mg - 45mg PO in 24 hours Clomethiazole 1 tb -3 tbs PO in 24 hours - in case of anxiety/depression: Trazodone 25 mg – 150 mg PO in 24 hours Escitalopram 10 mg – 20 mg PO in 24 hours Mirtazapine 15 mg – 45 mg PO in 24 hours

Citalopram 10 mg - 20 mg PO in 24 hours

Paroxetine 20 mg – 50 mg PO in 24 hours

The control group is treated with psychopharmacological therapy, defined by the PI, according to the Evidence Based Medicine criteria.

Patient can withdraw the ICF at any time.

The investigators could decide to withdraw a patient for safety and health.

The withdrawn patients will not be evaluated unless they have been treated for 8 days, useful to evaluate the aromatherapy efficacy.

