6. PROJECT OBJECTIVES

The goal of this project is to evaluate the effectiveness of aromatherapy in air diffusion in addition to psychotropic drugs in order to evaluate a possible reduction in BPSD.

The project's hypothesis is that GROUP B patients show an improvement in their BPSD. The performed neuropsychological tests will provide the answer to the project hypotesis.

Primary objectives: validate the hypothesis that the use of aromatherapy in air diffusion can improve the BPSD management, allowing a reduce in psychotropic therapy prescribed and its secondary side effects. The patient's nurses will be tested with NPI-NH, that will characterize

frequency and seriousness of BPSD [15,16, 17]. A score greater or equal to 1 is considered positive for presence of BPSD.

Secondary objectives: validate the hypothesis that the use of aromatherapy will improve the management of BPSD patients, with a simultaneously reduction of physicians, nurses and care assistants stress. The last aspect will be evaluated with a specific part of NPI-NH test. The decrease of the initial score represented an improvement [19.20]. The NPI-NH test will be performed according to the time points defined in paragraph 7.1.1

The obtained results could be interesting to the future implementation of the use of essential oils in air diffusion in acute geriatric departments and in all facilities with BPSD patients.

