8. PROJECT DESIGN

The project will be managed in the acute geriatric department of the Clinica Luganese Moncucco. Enrolment and treatment scheme is present in the flow chart (chapter 2).

After randomization patients will be enrolled in the two groups GROUP A, control group, and GROUP B, treatment group.

The enrollment will be performed in 2 months.

GROUP A: 16 patients, following the inclusion criteria, will be enroll and they will be treated with psychotropic drugs.

GROUP B: 16 patients, following the inclusion criteria, will be enroll and they will be treated with psychotropic drugs and, in a complementary way, with aromatherapy in environmental diffusion.

The project hypothesis will be validated using the following neuropsychological and functional tests:

- CAM (Confusion Assessment Method);
- CDR (Clinical Dementia Rating Score)
- MMSE (Mini Mental State Examination);
- FAB (Frontal Assessment Battery);

- Tinetti's scale;
- BADL (Basic Activities of Daily Living);
- IADL (Instrumental Activities of Daily Living);
- NPI-NH (Neuropsychiatric Inventory Nursing Home Version);

Neuropsychological tests are part of clinical practice [18].

Scientific reports show that essential oils in air diffusion are effective in 3 days. A final timepoints of 14 days represent the mean hospital stay:

2 days for the collection of behavioral data;

6 days to observe the possible effectiveness of aromatherapy in air diffusion;

6 days to adapt the therapy with oils and psychotropic drugs and stabilize patient's condition for a possible discharge.

Enrolled patients and nurses will be tested according to the following times:

8.1.1 Observation for 48 hours with data collection and execution of the NPI-NH (T1): in the 48 hours after patient admission at the Geriatric Department or at the diagnosis of dementia, the information collection will be performed: sensitive data (age, gender), dementia condition (CAM, CDR, MMSE, FAB), functional status (IADL, BADL, Tinetti scale) and the used number of psychotropic drugs. As a result of this evaluation, patient will be assessed for the presence of BPSD using the NPI-NH assessment scale, nurses will be undergo to NPI – NH test within 48 hours after patient admission. In case of a score greater than or equal to 1, patient will be followed within the study project, otherwise it will follow the standard process.

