13. STATISTICAL CONSIDERATIONS

This is a pilot study which required the enrollment of 32 patients. For this reason, the statistical considerations will be purely descriptive.

Patients will be enrolled, according to the described randomization, in GROUP A, control group in which patients will be treated exclusively with traditional psychotropics drugs, or in group B, in which they will be treated with aromatherapy integrated with psychotropics drugs.

14.ETHICS CONSIDERATIONS

This protocol has been designed and written in accordance with the Helsinki Agreement, the International Good Clinical Practice ICH Guidelines and the arrangements of the European and Swiss regulatory authorities [23, 24, 25].

In consideration of the presence of potentially vulnerable subjects, in order to ensure the inalienable principle *of patient autonomy* (I principle of Medical Ethics), informed consent will be explained and requested to a relative/legal representative of the patient who has lost the ability to discern.

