## Statistical methodology

The Mann-Whitney test has been used to evaluate the statistical significance of the difference between the variations in scores (T3 - T1) regarding the two interest groups of patients (control and treated). The Mann-Whitney test has been used instead of the t-test for independent samples as the scores variations distributions between T1 and T3 are not Gaussian, with the exception of the "thymic" area.

The statistical significance of the differences between the variations in scores  $(T_3 - T_1)$  has been further explored using a linear regression model to account for the initial CIRS comorbidity index (that resulted slightly higher in the control group); it should be noted that Huber-Sandwich robust standard errors have been used because of the presence of heteroskedasticity. Moreover, because of the relatively reduced number of observations available, the estimate has been repeated using the median regression model to check the robustness of the results. Both estimates (not presented here for convenience) confirmed the results obtained with the Mann-Whitney test.

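### The protocol plans a descriptive pilot analysis, but the SAP text tests T3-T1 changes for significance in what reads as several areas, with no exploratory label or multiplicity control in that text

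*SAP*

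**What the plan says.** **Protocol, analysis.** Section 5 says: "As the project is a pilot study, a descriptive analysis will be performed". Section 13, after giving the 32 patients, says: "For this reason, the statistical considerations will be purely descriptive". No test, significance level, primary area or comparison visit is named.

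**Protocol, outcome.** In the Synopsis, "the improvement of the score is represented from decrease of the NPI-NH respect to the initial assessment". NPI-NH is scheduled at T1, T2, T3 and T4 (sections 5 and 8). The section 8 timetable allots "6 days to observe the possible effectiveness of aromatherapy in air diffusion", followed by "6 days to adapt the therapy with oils and psychotropic drugs" before the final assessment.

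**Protocol, hypothesis wording.** The Synopsis (secondary objectives) and sections 6 and 8 also speak of validating a hypothesis through the tests.

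**SAP, Statistical methodology.** "The Mann-Whitney test has been used to evaluate the statistical significance of the difference between the variations in scores", the variations being T3 minus T1. The section says the change distributions were non-Gaussian except in one area, called thymic. It then adds a linear regression on the CIRS comorbidity index with robust standard errors, and a median regression. Both are said to confirm the Mann-Whitney results, but their estimates are not shown.

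**The concern.** A reader who takes the protocol at its word expects summaries by arm. The SAP text offers significance statements, and nothing in it marks them as exploratory or as going beyond the protocol. Since one area is singled out as an exception, more than one was apparently examined. If so, any single significant area has to be read against the number tested, which that text does not give. The reader also sees one follow-up visit out of three.

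The stakes lie in how firm the results look. Section 6 of the protocol says: "The obtained results could be interesting to the future implementation of the use of essential oils in air diffusion" in acute geriatric departments and in other facilities caring for such patients. A significance claim from about 16 patients per arm could carry more weight there than a descriptive pilot supports.

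**Working it through.** **1. What can be reproduced.** The documents give no alpha, sidedness, power, effect size or SD, so there is no statistical figure to rebuild. The randomisation list in section 7 can be counted: 8 blocks of 4 give 32 patients, 16 A and 16 B, as stated.

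**2. Inputs.**
- From the documents: 16 planned per arm (section 7); Mann-Whitney on T3-T1 (SAP); 12 NPI-NH domains on the form (appendix 21.1.7: 10 in the total score plus 2 others).
- Assumed: two-sided 0.05 per area; all 16 per arm analysed at T3; k = 2, 3, 4 or 12 areas; correlation between areas of 0, 0.5 or 0.8.

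**3. Size of one test.** From the exact null distribution of U for 16 v 16, P(two-sided) is 0.0468 at U ≤ 75 and 0.0513 at U ≤ 76. The test therefore rejects at U ≤ 75, with true size 0.0468.

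**4. Chance of at least one false-positive area.** For independent areas it is 1 − (1 − 0.0468)^k:
- k = 2: 1 − 0.9532² = 0.091
- k = 3: 1 − 0.9532³ = 0.134
- k = 4: 1 − 0.9532⁴ = 0.175
- k = 12: 1 − 0.9532¹² = 0.437

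For correlated areas, by simulating normal changes with the same cut-off (100,000 runs):

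| Areas | Correlation 0 | 0.5 | 0.8 |
|---|---|---|---|
| 2 | 9.1% | 8.7% | 7.7% |
| 3 | 13.4% | 12.2% | 9.8% |
| 4 | 17.5% | 15.2% | 11.4% |
| 12 | 43.7% | 31.7% | 19.3% |

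Tied scores built from frequency × severity products matter little. Simulated test size was 0.046 to 0.049, which for independent areas gives 9-10%, 13-14% and 17-18% for k = 2, 3 and 4.

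**5. Would a Holm correction at T3 repair this?** The first Holm step rejects at U ≤ 68, 64 and 62 for k = 2, 3 and 4 (sizes 0.0234, 0.0152, 0.0121). For independent areas:
- k = 2: 1 − (1 − 0.0234)² = 0.046
- k = 3: 1 − (1 − 0.0152)³ = 0.045
- k = 4: 1 − (1 − 0.0121)⁴ = 0.048

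That control requires T3 and the areas to have been fixed beforehand. If the visit were picked by result from T2, T3 and T4, simulation gives about 10-12% for 2 to 4 areas (assumed correlation 0.5-0.7 between visits and 0-0.5 between areas).

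**6. What 16 per arm can show.** The 95% Hodges-Lehmann interval for the arm difference has a mean half-width of 0.75 SD for normal changes, and 0.55 to 0.67 SD for four skewed or heavy-tailed shapes. Intervals show that imprecision; a bare significance statement does not.

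**The case against.** **Part of the SAP was not available.** One portion was removed before this review. What remains is a single section in the past tense that reads like an extract from a report. A count of areas, a multiplicity rule or an exploratory label may stand elsewhere. This stands, and it limits every statement about absence to the text available. The number of areas is itself inferred from one phrase.

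**The protocol does not prohibit testing.** A reader might infer that it rules out significance tests. It does not say so, and its repeated talk of validating a hypothesis points the other way. What holds is that it commits twice to a descriptive analysis and names no test. The protocol's own wording therefore also needs reconciling.

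**T3 is a sensible visit.** It closes the 6-day effectiveness window, and T4 follows a period of therapy adaptation. A reader might infer that T3 was picked for its result; nothing in the documents shows that. They simply do not name it.

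**The methods are conventional.** A rank test for non-Gaussian changes and robust errors under heteroskedasticity are ordinary choices, and the regressions are presented as further exploration. A reader might infer that CIRS was added after the imbalance was seen. It is absent from the baseline list in section 8.1.1 ("dementia condition (CAM, CDR, MMSE, FAB), functional status (IADL, BADL, Tinetti scale) and the used number of psychotropic drugs"), and the SAP remarks that it was slightly higher in controls. But the text does not say when the adjustment was chosen. This is missing detail and does not carry the point.

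**Conclusion.** The point holds as a mismatch between a protocol that promises description and a SAP text that reports significance. That text has no exploratory label or error control, and it omits T2 and T4. Confidence is high for the mismatch and lower for what the text leaves out.

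Under the stated assumptions, the chance of at least one false-positive area is about 7.5-9% for two areas, 9.5-13% for three and 11.5-17.5% for four. All 12 domains would give about 19-44%. These rates are illustrative. They move with alpha, the number of areas, their correlation and the numbers analysed, none of which is given. The 12-area figure is an upper case, not a claim that 12 were tested.

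None of this shows that a reported result is false, since the text shows none. It should be fixed, because the fix changes what may be concluded at almost no cost.

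**What to change.** 1. Reconcile the protocol and SAP wording. Make no significance claim, and label every p-value exploratory and not pre-specified in the protocol.
2. Report arm differences with 95% confidence intervals for total NPI-NH and for every area tested, at T2, T3 and T4, with numbers assessed per arm, labelled descriptive. Doing so means listing the areas and the domains in each.
3. Wherever the CIRS-adjusted and median regressions are said to confirm the result, show their estimates with confidence intervals.
4. Do not rescue a claim with Holm at T3 unless a record shows that T3 and the areas were fixed before the data were seen.

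**Cost.** Reporting only, from assessments the protocol already schedules; no new patients or visits. The number of intervals is (areas + total) × 3 visits: (2+1)×3 = 9, (4+1)×3 = 15, and (12+1)×3 = 39 if every domain was tested. The downside is more table rows and the possible loss of a significance claim, if one was made.

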8.1.2 Assessment of NPI-NH at T2 (T1-3 days): 3 days after enrollment, patient will be re-evaluated with NPI-NH to assess BPSD progress. In addition, the distress level of on the three health caregivers is also measured with the NPI-NH test.

8.1.3 Assessment of NPI-NH at T3, assessment of vital parameters and use of drug reserves (T1-6 days): 6 days after enrollment, NPI-NH will be re-executed, with associated assessment of patient's vital signs (PAS, PAM, FC) and the use of psychotropic drug reserves.

8.1.4 Final T4 assessment (T1-12 days): NPI-NH scale will be performed in association with vital signs.

The physician in charge of dispensing the NPI-NH questionnaires to nurses to collect BPSD patients status, will also submit the questionnaires to the referring physician, nurse and care assistants with the aim to assess the level of stress in the clinical staff (see "Distress" column in NPI-NH questionnaire in the appendix).

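### The SAP tests only the T3 − T1 change and gives no reason, so T2 and T4 should be shown beside it, T3 labelled exploratory, and the 8-day rule kept out of the main comparison

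*SAP*

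**What the plan says.** **Schedule.** Protocol Section 5 places T1 within 48 hours of admission or at the first appearance of BPSD, then T2 "3 days after enrollment, at T3 (T1-6 days) 6 days after enrollment, at T4 (T1-12 days) at 14th day". Section 8 repeats this, from 8.1.2 ("3 days after enrollment, patient will be re-evaluated with NPI-NH to assess BPSD progress") to 8.1.4 ("8.1.4 Final T4 assessment (T1-12 days): NPI-NH scale will be performed in association with vital signs").

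**Phases.** Section 8 divides the 14 days, which it equates with the mean hospital stay, into three parts: "2 days for the collection of behavioral data", then "6 days to observe the possible effectiveness of aromatherapy in air diffusion", then "6 days to adapt the therapy with oils and psychotropic drugs and stabilize patient's condition for a possible discharge".

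**Planned analysis.** Section 13 of the protocol limits the statistics to description. No section names a primary time point, a test or an error rate.

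**Withdrawals.** Section 5 adds: "The withdrawn patients will not be evaluated unless they have been treated for 8 days, useful to evaluate the aromatherapy efficacy". It explains the 8 days as 3 days to effect plus 5 further treatment days.

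**SAP.** The Statistical methodology section applies a Mann-Whitney test to "the difference between the variations in scores (T 3 - T 1 ) regarding the two interest groups of patients", then a linear regression adjusted for CIRS with robust standard errors, then a median regression. It mentions neither T2 nor T4, gives no reason for T3 and defines no analysis set.

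**The concern.** Three post-baseline changes were planned and one was tested. The SAP is in the past tense: it picks the test from observed distributions, adjusts for a comorbidity index because it turned out higher in the control group, and reports that further models agreed. CIRS is not among the assessments listed in protocol Sections 5 and 8. A reader therefore has no record that T3 was fixed before the results were known, and cannot tell from this text whether any difference was already present at T2 or lasted to T4.

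The second issue is who is counted. If the 8-day rule decides who enters a comparison made at 6 days, patients can be excluded for something that happened after randomisation, and in some cases after the endpoint was measured. Withdrawal may depend on both arm and symptoms, so such exclusions would bias the randomised comparison. In a study planned for 16 per arm, even one or two would matter.

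**Working it through.** **1. The calendar.** Inputs are the phase lengths in Section 8 and the visit offsets in Sections 5 and 8. I read the protocol's notation T1-6 days as T1 plus 6 days, and place T1 at the end of the 2-day collection period.

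- Phases: 2 + 6 + 6 = 14 days, which reproduces the stated final time point.
- T1 = day 2; T2 = 2 + 3 = day 5; T3 = 2 + 6 = day 8; T4 = 2 + 12 = day 14.
- The effectiveness window runs from day 2 to day 8 and ends at T3. The adaptation phase runs from day 8 to day 14 and ends at T4.

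**2. The 8-day rule against T3.**

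- Basis of the rule: 3 + 5 = 8 treated days.
- With treatment counted from T1, 8 treated days end at 2 + 8 = day 10, two days after T3 and four before T4.
- A patient withdrawn on treatment day 6 or 7 could therefore have a T3 score and still not be evaluated under the literal rule.
- If the 2 collection days were counted, 2 + 6 = 8 and T3 would meet the rule exactly. The protocol's wording refers to days treated, so this reading is possible but not the natural one.

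**3. What an unplanned choice among three visits could cost.** The documents give no alpha and no correlation between the changes, so both are assumed: two-sided alpha 0.05 and a common correlation ρ between the three arm contrasts.

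- Independent contrasts: 1 − (1 − 0.05)³ = 1 − 0.857 = 14.3%.
- Correlated contrasts: 1 − ∫ φ(u) [Φ((1.96 − √ρ·u)/√(1−ρ)) − Φ((−1.96 − √ρ·u)/√(1−ρ))]³ du.

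| Assumed ρ | Chance that at least one of three is nominally significant, with no true effect |
|---|---|
| 0.4 | 13.1% |
| 0.5 | 12.5% |
| 0.6 | 11.8% |
| 0.7 | 10.9% |
| 0.8 | 9.8% |
| 0.9 | 8.4% |

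A simulation with the SAP's own test (Mann-Whitney, 16 per arm, normal changes, 10,000 runs) gives 12.2% at ρ = 0.5, 10.5% at 0.7 and 7.9% at 0.9. The two approaches agree on roughly 8% to 13% over ρ from 0.9 to 0.4.

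**The case against.** The strongest reply is that T3 has a basis in the protocol: it closes the period set aside for observing effectiveness. The six days after it are for adapting oils and drugs before discharge, so T4 is a less clean add-on comparison. T3 is also the only follow-up visit for which 8.1.2 to 8.1.4 list the use of drug reserves. This stands as a possible rationale. The SAP does not invoke it, however, and nothing dated shows that it guided the choice.

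Three stronger readings are tempting, and the documents do not support them.

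- *T3 was picked because it looked best.* The SAP was written with data in view, but nothing shows that T2 or T4 was tested and set aside. The error rates above describe what selection would cost, and the study was planned as descriptive, with no error rate to protect.
- *Collected data were thrown away.* T2 and T4 were planned, but no document says how many scores were obtained. Day 14 is the mean stay, so some patients may have left before T4. The two visits may also have been summarised descriptively outside the short SAP text.
- *The T3 analysis breaks the 8-day rule.* The rule concerns withdrawn patients only, calls 8 days useful rather than necessary, and sets no analysis time. The SAP does not say that it was applied or that anyone was excluded.

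It is also tempting to conclude that T4 should have been the main endpoint because it is called final. Final is not primary. Choosing T4 now would be just as unplanned, and T4 is the visit most exposed to missing data from discharge.

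**Conclusion.** The point holds in a limited form. The SAP text tests one of three scheduled changes without a reason, and T3 cannot be shown to be a prior choice. If the best visit had been chosen, a nominal 5% would be about 8% to 13%; this rests on an assumed alpha of 0.05 and equal correlations of 0.9 to 0.4. It measures a risk and does not show that selection occurred.

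The 8-day rule and a T3 at 6 days are not reconciled. Read literally, with treatment counted from T1, the rule could remove patients who have the tested score. Whether it did so is unknown. All of this assumes that T3 in the SAP is the protocol's T3, which the SAP does not define.

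The T3 result is not invalidated. It should be read as exploratory until the other visits and the analysis set are shown.

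**What to change.** 1. **Show all three visits.** Report the arm difference in NPI-NH change with 95% CI at T2, T3 and T4, adjusted for the T1 score, with the number observed per arm at each visit. Use a method suited to the non-Gaussian, heteroskedastic changes that the SAP reports: either a longitudinal model with robust or bootstrap standard errors, or the same Mann-Whitney test and robust regression at each visit, with the T1 score added to the regression.
2. **Label T3 − T1 as exploratory**, unless a dated record of a prior choice exists. If the 6-day window was the reason, say so. Do not promote T4 to main contrast after the fact.
3. **State the analysis set.** Include every randomised patient with at least one post-T1 score, in the allocated group, whatever the number of treatment days. Say how the 8 days are counted and how many patients the rule affects, and show the 8-day evaluable set only as a sensitivity analysis.

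The cost is some SAP text and a little more analysis of whatever T2 and T4 scores exist. T4 may be incomplete and its interval wide, which the numbers per arm will show. The T3 result is no longer the sole evidence.
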